6.1 Disposition of Subjects

Disposition of subjects will be summarized for overall and by center. Subject study duration and reason for discontinuation will be tabulated with the count and percent of enrolled subjects in each category of study duration or discontinuation reason.

6.2 Demographic and Baseline Characteristics

Summary statistics for demographic and baseline disease characteristics will be calculated (by gender for demographic characteristics) for all subjects enrolled. Demographic characteristics include age, race, ethnicity, body weight, height and body mass index. Baseline disease characteristics include time to diagnosis of Schizophrenia disease, [REDACTED]

[REDACTED] Summary statistics will consist of mean, median, range, and standard deviation (SD) for continuous variables and tabulations of frequency distributions for categorical variables.

7 Efficacy Analyses

7.1 Primary Efficacy Analysis Endpoint

The primary endpoint of this trial is the comparison of inpatient psychiatric hospitalization rates (proportion of subjects with ≥ 1 inpatient psychiatric hospitalization[s]) between the retrospective period (Months 1 to 3) while on oral standard-of-care antipsychotic treatment and the prospective period (Months 1 to 3) after the switch to Abilify MyCite. Primary analysis will use the mITT for Month 1 to 3.

7.1.1 Statistical Methods of Primary Efficacy Analysis

The primary analysis will be achieved by testing for statistically significant (at 2-sided overall alpha = 0.05). The analysis will be performed using a McNemar test on those who have hospitalization data during Months 1 to 3 prior to the screening period and during Months 1 to 3 after switch to Abilify MyCite.

Protocol 31-201-301 Interim Analysis Plan

7.1.2 Technical Details

Inpatient psychiatric hospitalization is defined as closed (locked) ward or open ward inpatient psychiatric hospitalization, where the hospitalization is not primarily for psychosocial reasons.

The start date and end date of the retrospective period Months 1-3 are calculated in the following ways: start date = (Date signing informed consent - 28*6 Days) and end date = (Date of signing informed consent - 28*3-1 Days). The start date and end date of the prospective period Months are calculated as: start date = (Mycite start date) and end date = (Mycite start date + 28*3 - 1). Similarly, the start date and end date of the retrospective period Months 4-6 are calculated in the following ways: start date = (Date signing informed consent - 28*3 Days) and end date = (Date of signing informed consent -1 Days). The start date and end date of the prospective period Months are calculated as: start date = (Mycite start date + 28*3) and end date = (Mycite start date + 28*6 - 1).

Inpatient psychiatric hospitalization is deemed to occur during the retrospective (or prospective) Months 1-3 if:

- The hospitalization starts before the start date of retrospective (or prospective) Months 1-3 and continues into Months 1-3
- The hospitalization starts during the retrospective (or prospective) period.

Similarly, Inpatient psychiatric hospitalization is deemed to occur during the retrospective (or prospective) Months 4-6 if:

- The hospitalization starts before the start date of retrospective (or prospective) Months 4-6 and continues into Months 4-6
- The hospitalization starts during the retrospective (or prospective) period

All the above hospitalization in Months 1-3 and Months 4-6 will be counted in the Month 1-6 period.

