3.5 Endpoints

3.5.1 Primary Endpoint

The primary endpoint is the comparison of inpatient psychiatric hospitalization rates (proportion of subjects with ≥ 1 inpatient psychiatric hospitalization) between the retrospective period (Month 1 to 3) while subjects are on oral standard-of-care antipsychotic treatment and the prospective period (Month 1 to 3) after the subjects switch to Abilify MyCite.

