7.1 Sample Size

The primary endpoint of this trial compares the paired proportions of inpatient psychiatric hospitalization during the retrospective period (Month 1 to 3) and the prospective period (Month 1 to 3), which will be analyzed using a McNemar test.

Based on published results of other similar studies for the particular time periods (retrospective Month 1 to 3 and prospective Month 1 to 3)^{23,24} we are evaluating, it is reasonable to assume that 15.5% of subjects are hospitalized during retrospective Month 1 to 3 and 7% are hospitalized during prospective Month 1 to 3; about 5% of subjects who are not hospitalized retrospective will be hospitalized prospective, while 13.5% of subjects who are hospitalized retrospective will not be hospitalized. With this assumption, 200 completed subjects will provide 80% power (alpha = 0.05 two-sided) to detect a difference of 8.5% in 2 paired hospitalization proportions between pre-switch and post-switch periods while the proportion of total discordant pairs is 18.5%. In addition, this sample size will provide 80% power for the comparison of retrospective Month 4 to 6 vs prospective Month 4 to 6, assuming 30% of the subjects are hospitalized pre-switch (12.5% subjects will be hospitalized post-switch and another 17.5% won't have hospitalization post-switch) and, overall, 20% are hospitalized post-switch (among them, 12.5% subjects are hospitalized both pre-switch and post-switch and 7.5% have no hospitalization pre-switch).

Two interim analyses are planned at when 50% and 70% of subjects have completed the prospective period (Month 1 to 3); in order to conserve the overall Type I error at 0.05 level, 224 to 300 evaluable subjects are needed to complete the 3-month treatment to maintain 80% power. This sample size assumes the 3 sequential tests are made using LanDeMets Spending Function²⁵ with O'Brien-Fleming boundary, a futility conditional power of 15% is built in the sample size calculation to allow the trial to stop for futility. Based on the conditional power and the alpha level at the interim analysis, the trial could stop for efficacy or futility, continue with initially planned 224 sample size or increase to up to 300 if the conditional power fall between 30% to 80% (Section 7.4.4). The 2-sided alpha levels for these 2 interim analyses are 0.00312 and 0.0139 respectively, and the alpha left for the final analysis will be 0.04528.

Protocol 031-201-00301

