3.3 Study Population

The study population will include male and female subjects, 18 to 65 years of age, inclusive, with a diagnosis of schizophrenia according to DSM-5 criteria. Subjects must have had at least 1 inpatient psychiatric hospitalization within the 4 years (48 months) prior to screening but must not have been hospitalized for any psychiatric reason during the 4 weeks prior to signing the ICF or at any time during the screening period. Subjects must have been on oral antipsychotics treatment in the last 7 months prior to screening.

4 Sample Size and Power Justification

The primary endpoint of this trial compares the paired proportions of inpatient psychiatric hospitalization during the retrospective period (Month 1 to 3) and the prospective period (Month 1 to 3), which will be analyzed using a McNemar test.

Based on published results of other similar studies for the particular time periods

Protocol 31-201-301 Interim Analysis Plan

(retrospective Month 1 to 3 and prospective Month 1 to 3) we are evaluating, it is reasonable to assume that 15.5% of the subjects are hospitalized during retrospective Month 1 to 3 and 7% are hospitalized during prospective Month 1 to 3; about 5% of subjects who are not hospitalized retrospective will be hospitalized prospectively, while 13.5% of the subjects who are hospitalized retrospectively will not be hospitalized. With this assumption, 200 completed subjects will provide 80% power ($\alpha = 0.05$ two-sided) to detect a difference of 8.5% in the paired hospitalization proportions between pre-switch and post-switch periods while the proportion of total discordant pairs is 18.5%. In addition, this sample size will provide 80% power for the comparison of retrospective Month 4 to 6 vs prospective Month 4 to 6, assuming 30% of the subjects are hospitalized pre-switch (12.5% subjects will be hospitalized post-switch and another 17.5% won't have hospitalization post-switch) and, overall, 20% are hospitalized post-switch (among them, 12.5% subjects are hospitalized both pre-switch and post-switch and 7.5% have no hospitalization pre-switch).

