7.4.1.2 Technical Details

Number of inpatient psychiatric hospital stays per subject during the 3 months (Months 1-3) of the retrospective (or prospective) period is determined as the total number of inpatient psychiatric hospitalization, closed (locked) ward or open ward, but not primarily for psychosocial reasons for each subject during the respective/retrospective periods. Cumulative duration of inpatient psychiatric hospitalization per subject is the sum of duration of each reported inpatient psychiatric hospitalization for each subject, which is defined as $\min(\text{Date of Discharge, End date of the 3-months of the respective period}) - \max(\text{Start Date of Admission, Start date of the 3-months of the respective period}) + 1$. Mean duration of inpatient psychiatric hospitalization per subject is derived as the cumulative duration divided by the number of inpatient psychiatric hospitalization for each subject. If a subject did not experience any inpatient psychiatric hospitalization during the 13-months, zero will be assigned to his/her number of inpatient psychiatric hospital stays, and to his/her cumulative and mean duration of inpatient psychiatric hospitalization. Similarly, method will be used to analyze the cumulative duration of inpatient psychiatric hospitalization and mean duration of inpatient psychiatric hospitalization during Month 1-6.

Inpatient hospitalizations for psychosocial reasons are defined as inpatient psychiatric hospitalization, closed (locked) ward or open ward, where hospitalization is primarily psychosocial reasons. For the last 3 months (Months 4-6) of the retrospective (or prospective) period, number and cumulative or mean duration of inpatient hospitalizations for psychosocial reasons are derived in similar ways to those of inpatient psychiatric hospitalization.

Number and cumulative or mean duration of inpatient non-psychiatric hospitalizations during the 3 months (Months 1-3) of the retrospective (or prospective) period are derived in similar ways to those of inpatient psychiatric hospitalization.

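### SAP 7.1.2 drops psychosocial admissions from the primary event, which the protocol endpoint does not, and no readable analysis for Months 1-3 counts them or puts them back

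*SAP*

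**What the plan says.** - **Protocol 3.5.1:** "The primary endpoint is the comparison of inpatient psychiatric hospitalization rates", measured as the proportion of subjects with at least one such admission in Months 1-3 of each period. The synopsis, 2.3.1 and 7.4.1 use the same event, and none of them sets aside a type of psychiatric admission.
- **SAP 7.1** repeats the protocol's wording. **Section 2.2 of the interim analysis plan** also states the endpoint without an exclusion.
- **SAP 7.1.2** defines the event as a closed-ward or open-ward psychiatric admission "where the hospitalization is not primarily for psychosocial reasons".
- **SAP 7.4.1.2** gives the rule for deriving the psychosocial admissions: "For the last 3 months (Months 4-6) of the retrospective (or prospective) period, number and cumulative or mean duration". The paragraphs before and after that rule, on psychiatric and non-psychiatric stays, use Months 1-3.
- **SAP 7.1.3** names one sensitivity analysis, on subjects who completed three months. **SAP Appendix 2** adds an ITT table of the same endpoint.
- **Protocol 3.6** gives the open-label design as its whole entry on avoiding bias.

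**The concern.** Whether an admission was primarily psychosocial is a judgement. In a mirror-image trial the comparison is between two periods for the same subject, so a judgement applied differently in the two periods goes straight into the treatment effect. The readable text does not say what makes an admission primarily psychosocial, who decides, or whether anyone decides without knowing the period. The retrospective admissions are collected at screening from past history; the prospective ones are recorded while the site knows that the subject is on MyCite.

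Events are few, so a handful of reclassified subjects can decide the result. A reader of the final report would want to know how many subjects lost event status in each period and whether the conclusion stands with them counted. The readable plan provides for neither.

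**Working it through.** **1. Inputs (protocol 7.1, SAP section 4).** The plan assumes "15.5% of the subjects are hospitalized during retrospective Month 1 to 3 and 7% are hospitalized during prospective Month 1 to 3". The discordant cells are 13.5% (retrospective only) and 5% (prospective only), a total of s = 18.5% and a difference of d = 8.5 points. The share hospitalized in both periods is 15.5 − 13.5 = 2%. The planned sample is 224 completers, and the final two-sided alpha is 0.04528.

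**2. The plan's own figure.** N = [z(0.975)·√s + z(0.80)·√(s − d²)]² / d²
= [1.960 × 0.4301 + 0.8416 × 0.4216]² / 0.007225 = 198.6, so 199 against the stated 200. Simulating 224 with the stated looks and a binding 15% futility rule gives 80.1% power. The sample size reproduces; it is not the issue here.

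**3. Number of events.** 224 × 0.155 ≈ 35 subjects with a retrospective event and 224 × 0.07 ≈ 16 with a prospective one. The expected discordant pairs are 224 × 0.135 ≈ 30 and 224 × 0.05 ≈ 11.

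**4. Sensitivity to a few reclassified subjects.** This is a chosen near-miss, not the planning scenario. z = (b − c)/√(b + c), where b is retrospective-only and c is prospective-only. A removed subject becomes a no-event/no-event pair.

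| Case | b vs c | z | p | Continuity-corrected p | Exact p |
|---|---|---|---|---|---|
| Nothing removed | 24 vs 13 | 11/√37 = 1.81 | 0.071 | 0.100 | 0.099 |
| Two prospective-only removed | 24 vs 11 | 13/√35 = 2.20 | 0.028 | 0.043 | 0.041 |
| Two from each side removed | 22 vs 11 | 11/√33 = 1.91 | 0.056 | 0.082 | 0.080 |
| Two retrospective-only removed | 22 vs 13 | 9/√35 = 1.52 | 0.128 | 0.176 | 0.175 |

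Only the second row crosses 0.04528. It does so with all three versions of the test, which matters because the SAP does not say which version it will use.

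**5. Range over assumed shares.** The documents give no share of psychosocial admissions. Suppose that a share qr of subjects with a retrospective event and qp of those with a prospective event lose event status, independently. The discordant cells become
p10′ = p10(1 − qr) + p11(1 − qr)qp and p01′ = p01(1 − qp) + p11(1 − qp)qr.

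*Equal removal under the planned effect, N = 224, alpha 0.04528, no interim looks:*

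| qr = qp | p10′, p01′ | Difference | Power | Fixed-design N for 80% (alpha 0.05) |
|---|---|---|---|---|
| 0 | 13.5%, 5.0% | 8.5 points | 83.5% | 199 |
| 10% | 12.33%, 4.68% | 7.65 points | 78.5% | 226 |
| 20% | 11.12%, 4.32% | 6.8 points | 72.5% | 260 |

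The type I error stays at about 0.049. The power loss applies only if the planning rates refer to all psychiatric admissions, which the documents do not say.

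*Unequal removal with no true effect (15.5% in both periods, 2% in both), single test at 0.05, N = 224:*

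| qr | qp | Chance of rejection |
|---|---|---|
| 0 | 10% | 0.073 |
| 0 | 20% | 0.152 |
| 10% | 30% | 0.164 |
| 0 | 30% | 0.298 |
| 10% | 0 | 0.073 |
| 20% | 0 | 0.152 |

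The last two rows push the result against MyCite by as much as the first two favour it.

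**The case against.** The best reply is that the protocol never defines a psychiatric hospitalization in its readable text, so the SAP supplies an operational definition where there was none. Leaving out admissions for social reasons may be clinically sensible. That is fair as far as it goes, but the protocol's silence is still a difference from SAP 7.1.2. Its only mention of social admissions is in the SAE definition (5.1), and its related/unrelated classification (3.7.1.4) is not tied to the endpoint.

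Three further objections limit the point:

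- **A reader might infer that the SAP never shows the excluded admissions for Months 1-3, or tabulates them only for Months 4-6.** The documents do not support this. The exploratory variable list is redacted, and 7.4.1.2 is a derivation rule, not a table. Its reference to Months 4-6 may be a drafting slip, given the Months 1-3 paragraphs around it. The readable table list has no psychosocial table for any period. Listings PDATA-13.1 and 13.2 cover hospitalizations in both periods, though the documents do not say that they show this classification.
- **A reader might infer that the exclusion favours MyCite.** Nothing supports a direction. The retrospective data are also recorded by the open-label site, no assessor is named for either period, and equal removal would cost power.
- **The example of 24 versus 13 is selected.** This stands. The planning assumptions imply about 30 versus 11, and removing two from each side does not cross the final alpha.

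**Conclusion.** The point holds in limited form. The primary event in SAP 7.1.2 is narrower than the one in the protocol endpoint, SAP 7.1 and the interim plan. The narrowing rests on a judgement with no readable criteria or assessor. The derivation of the removed admissions names the wrong window for checking the primary result, and neither of the readable extra analyses (completers, ITT) restores them.

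The size cannot be known from the documents. Two reclassified subjects can change a borderline result, and unequal removal of 10 percentage points from a base of zero would raise the type I error from 0.05 to about 0.073. Both figures rest on assumed counts or shares. They show that the check is worth having, not that the result will be biased. This is a low-severity point with a cheap remedy.

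**What to change.** 1. Use one definition of the primary event in the protocol, the SAP and the interim analysis plan. If the psychosocial exclusion stays, state its criteria and who applies them, in the same way for both periods.
2. Correct the derivation in SAP 7.4.1.2 to cover Months 1-3, and tabulate psychosocial admissions, and the subjects who lose event status because of them, for Months 1-3 by period.
3. Add a McNemar sensitivity analysis of the primary endpoint that counts all inpatient psychiatric hospitalizations in Months 1-3, on the same analysis sample as the primary test.

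The cost is a text change and two extra outputs. This assumes that the classification is recorded in the CRF: the SAP definition implies it, but no readable passage shows the field. No new subjects or visits are needed, and the planned sample size does not change.

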3.1 Type/Design of Trial

This is a phase 3b, open-label, prospective, clinical trial designed to assess the difference between inpatient psychiatric hospitalization rates in subjects on oral standard-of-care antipsychotic treatment(s) for a period of 6 months followed by a switch to Abilify MyCite for a period of 3 months (Months 1 to 3). At the Month 3 visit, the investigator should decide if subjects will continue on Abilify MyCite for an additional 3 months (Months 4 to 6) or switch to a standard-of-care treatment (eg, oral atypical antipsychotics or a long acting injectable [LAI]) for the duration of treatment.

Protocol 031-201-00301

This trial will include male and female subjects who are 18 to 65 years of age, inclusive, with a diagnosis of schizophrenia according to Diagnostic and Statistical Manual of Mental Disorders, Fifth Edition (DSM-5) criteria. Subjects must have had at least 1 inpatient psychiatric hospitalization within 4 years (48 months) and must have been prescribed oral antipsychotics for at least 6 months or longer prior to screening.

Subjects will enter a screening period (up to 45 days). If deemed eligible to participate, subjects will enter an open-label Abilify MyCite treatment prospective phase for up to 6 months.

Oral Standard-of-Care Antipsychotic Treatment(s) (Retrospective Phase)

To be eligible for trial participation, subjects must have been prescribed oral antipsychotic standard-of-care pharmacotherapy for at least 6 months or longer, with evidence of prescription (ie, pharmacy records) during the retrospective phase and prior to screening. Subjects administered antipsychotics other than aripiprazole must cross-titrate onto oral aripiprazole during the screening period at the discretion of the investigator to be eligible for trial participation.

Screening

After providing informed consent, subjects will enter the 45-day (Days -45 to -1; approximately 6 weeks) screening period to determine if they are eligible to enter the Abilify MyCite treatment (prospective) phase. The subject's past psychiatric history for the 6 months prior to screening must be available, inclusive of a comprehensive review of all psychiatric hospitalizations and interventions (psychiatric only).

As safety of the subject dictates, 2 options are available to the investigator as subjects transition from the screening period to the Abilify MyCite treatment (prospective) phase:

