The purpose of the tolerability assessment/cross-titration is to evaluate for potential allergy to aripiprazole and the subject's clinical status prior to Abilify MyCite treatment. Subjects will be seen in the clinic for up to 45 days, until tolerability to oral aripiprazole has been determined, based on investigator discretion, or until the subject is terminated from the trial.

The recommended initial dose of oral aripiprazole is 10 mg or 15 mg/day, depending on the subject's symptoms and the investigator's judgment. The investigator may titrate the dose of oral aripiprazole up to 30 mg/day as deemed appropriate. Some investigators may choose this option for the subject depending as local practice patterns dictate and on the subject's safety.

Subjects may proceed to the Abilify MyCite treatment (prospective) phase after 1 week if they tolerate oral aripiprazole according to the investigator's judgment.^{16,17} If a subject cannot tolerate oral aripiprazole, or requires inpatient psychiatric hospitalization based on the investigator's clinical judgment, the subject will be withdrawn from the trial.

Subjects who routinely take their oral aripiprazole in the morning are not to take the oral dose on the morning of clinic visits, so that adjustments to the dose can be made, as required. Oral aripiprazole will be administered at the clinic after all assessments have been completed.

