3.9 Screen Failures

A screen failure subject is one from whom informed consent is obtained and is documented in writing (ie, subject signs an ICF), but who is not started on trial treatment. For the purposes of this trial, Abilify MyCite treatment begins with the first administration of Abilify MyCite on Day 1 of the prospective phase. Subjects who sign an eICF but who are not started on treatment are permitted to be re-screened. In the event that the subject is re-screened for trial participation, and the re-screening is not completed within the original screening window, a new eICF must be signed.

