5.2 Eliciting and Reporting Adverse Events

The investigator will periodically assess subjects for the occurrence of AEs from the time the eICF is signed until the end of the trial. For this trial, information on AEs will be followed for up to 7 months (including the safety follow-up period) after the first dose of Abilify MyCite has been administered. To avoid bias in eliciting AEs, subjects should be asked the non-leading question: “How have you felt since your last visit?” All AEs (serious and nonserious) reported by the subject must be recorded on the source documents and eCRFs provided by the sponsor. Serious AE collection is to begin after a subject has signed the eICF.

Use medical terminology in AE reporting. Adverse events should be reported as a single unifying diagnosis whenever possible or, in the absence of a unifying diagnosis, as individual signs or symptoms. Exacerbation or disease progression should be reported as an AE only if there are unusual or severe clinical features that were not present, or experienced earlier, or not expected based on the course of the condition.

In addition, the sponsor must be notified immediately by telephone, fax, or email of any IREs according to the procedure outlined below, in [Section 5.3](#). Special attention should be paid to recording hospitalization and concomitant medications.

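### Psychiatric admissions that begin and end between consent and Day 1 count in neither period, and cross-titrating subjects who need admission are withdrawn, so the primary result misses switch-related relapse before Day 1

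*SAP*

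**What the plan says.** **Windows.** SAP 7.1.2 (Technical Details) sets retrospective Months 1-3 as "start date = (Date signing informed consent - 28*6 Days) and end date = (Date of signing informed consent - 28*3-1 Days"), and retrospective Months 4-6 as the 84 days after that, ending the day before consent. The prospective side is anchored to the first MyCite dose instead: "The start date and end date of the prospective period Months are calculated as: start date = (Mycite start date"). In full, prospective Months 1-3 are "start date = (Mycite start date) and end date = (Mycite start date + 28*3 - 1"). A stay also counts in a period if "The hospitalization starts before the start date of retrospective (or prospective) Months 1-3 and continues into Months 1-3".

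**What lies between.** Protocol 3.1 states that after consent "subjects will enter the 45-day (Days -45 to -1; approximately 6 weeks) screening period". The same section places tapering, discontinuation and cross-titration of other antipsychotics in that interval.

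**Who leaves.** Protocol 3.2.1 provides for withdrawal from the trial: "If a subject cannot tolerate oral aripiprazole, or requires inpatient psychiatric hospitalization based on" the investigator's judgment. Under Protocol 3.9 a consented subject who never starts MyCite is a screen failure. It adds: "Subjects who sign an eICF but who are not started on treatment are permitted to be re-screened".

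**Who bypasses cross-titration.** Under Protocol 3.2.1, subjects on aripiprazole monotherapy, and subjects on another antipsychotic who have tolerated aripiprazole before, may go straight to MyCite. Others may move on after one week if they tolerate it.

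**Eligibility.** SAP 3.3 bars subjects with a psychiatric admission during screening. The current exclusion criteria in Protocol 3.4.3 contain no such bar.

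**Data.** Protocol 5.2: "Serious AE collection is to begin after a subject has signed the eICF".

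**The concern.** The trial is presented as a comparison of oral standard of care with the period after the switch. For subjects who need cross-titration, the change of drug is made before the post-switch window opens. An admission contained in that interval is not an event, and a cross-titrating subject who needs one is removed. Entry to the prospective window is thus partly conditional on having come through the change without needing admission. Nothing equivalent is asked of the retrospective window, which counts every admission in its 84 days.

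The filter acts on one side of a paired comparison and favours MyCite. The design is open-label with no concurrent control, so no other arm would show the loss. The planned analyses do not restore it. The sensitivity analysis in SAP 7.1.3 narrows the mITT further, to subjects at least 75 days in study. The ITT version of the primary table (CT-5.1.2, SAP Appendix 2) does not help either, because a subject withdrawn before Day 1 has no MyCite start date and so no prospective window.

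**Working it through.** **1. The calendar.** With consent as day C and the first MyCite dose as Day 1, SAP 7.1.2 gives:

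| Interval | Days | Counted as |
|---|---|---|
| C-168 to C-85 | 84 | Retrospective Months 1-3 (primary) |
| C-84 to C-1 | 84 | Retrospective Months 4-6 |
| Consent to the day before Day 1 | up to 45 | Nothing |
| Day 1 to Day 1 + 83 days | 84 | Prospective Months 1-3 (primary) |

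The two primary windows are equal in length. Up to 84 + 45 = 129 days separate them, of which the screening days belong to no period.

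**2. Which relapses are missed.**
- Stay begins and ends in screening: not counted.
- Admission needed during tolerability assessment or cross-titration: subject withdrawn, no prospective window, no pair for the McNemar test.
- Stay begins in screening and is still running on Day 1: counted as prospective.
- Relapse after Day 1, including after a one-week tolerability check: counted.
- Relapse in a direct switcher after Day 1: counted.

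The last three reach the primary test only if the subject meets the mITT rule in SAP 5.1.1 (at least 80% of medication taken and complete hospitalization data).

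**3. The plan's own figure.** Protocol 7.1 gives discordant cells of 13.5% and 5%, so s = 0.185 and d = 0.085.

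n = [1.960·√s + 0.8416·√(s − d²)]² / d² = [1.960·0.4301 + 0.8416·0.4216]² / 0.007225 = 198.6

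This agrees with the stated 200 completers for 80% power. The sample size is not in question.

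**4. Scale of admissions in a gap of this length.** The documents give no admission rate for screening. As an assumption, apply the plan's 84-day rates at constant hazard: 1 − (1 − p)^(t/84).

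| Gap | p = 7% | p = 15.5% |
|---|---|---|
| 7 days | 0.6% | 1.4% |
| 45 days | 3.8% | 8.6% |

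These are background rates. They are not excess relapse due to switching, nor the net change in the primary comparison.

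**5. How many it would take.** At N = 224 the planning case gives 0.135 × 224 = 30.24 and 0.05 × 224 = 11.2 discordant subjects. McNemar Z = (b − c)/√(b + c). Add k net subjects to the prospective-only cell:

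| k | Z | Two-sided p |
|---|---|---|
| 0 | 19.04/√41.44 = 2.958 | 0.0031 |
| 5 | 14.04/√46.44 = 2.060 | 0.039 |
| 6 | 13.04/√47.44 = 1.893 | 0.058 |

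The final-look level is 0.04528, so six suffice. Protocol 3.3 expects 493 − 320 = 173 subjects to be lost between screening and enrollment, for all reasons; six is 3.5% of them.

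**The case against.** **The window is declared.** Protocol 7.4.1 and SAP 7.1.1 define the comparison as the months before screening against the months after the switch to MyCite. Screening is a run-in on ordinary oral aripiprazole, and counting it answers a somewhat different question. This stands, and it is why the primary analysis should stay as it is.

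**Switch-related relapse is not shut out.** A reader might infer that relapse caused by switching can never reach the primary result. The documents do not support that: direct switchers, relapse after Day 1 and stays straddling Day 1 all count. Subjects already on aripiprazole monotherapy have no change of drug to relapse from.

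**The background rate is not the bias.** It is tempting to set 8.6% beside the 8.5-point design effect and conclude that the gap could cancel it. That figure assumes the full 45 days for everyone at the standard-of-care rate. In an equal-length window, gap admissions also displace later days rather than adding to them, so the net change could be much smaller.

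**Re-screening.** A reader might also infer that a failed-switch admission routinely moves into the primary retrospective count on re-screening. It does so only if part of the stay falls 85 to 168 days before the new consent. If nearer, it lands in retrospective Months 4-6. A new consent is required only when re-screening runs past the original window.

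**Withdrawals are not hidden.** SAP Appendix 2 lists disposition for the Enrolled Sample, adverse events for all enrolled subjects, and screening failures. These show that subjects left, but they do not re-estimate the endpoint.

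**Data may be incomplete.** Protocol 5.2 limits reporting of disease exacerbation as an adverse event, and the utilization record in Protocol 3.7.1.4 is centred on Day 1, which screening withdrawals never reach. This stands and shapes the fix.

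**Conclusion.** The point holds in limited form. The uncounted interval and the withdrawal rule are both in the text. Together they take switch-related relapse before Day 1 out of the post-switch side only, in MyCite's favour, and no planned analysis of the endpoint puts it back. Later relapse, relapse in direct switchers and straddling stays remain countable, so the loss is partial.

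The net bias cannot be computed from the documents, which give neither an admission rate for the gap nor the distribution of screening length. The 0.6% to 8.6% range rests on constant hazard and the plan's two rates, and indicates scale only. The firmer figure is the fragility one: if the data came out exactly as planned at 224 completers, about six net extra prospective-only admissions would turn a clear result (p = 0.003) into one that misses the final boundary (p = 0.058). That is few enough for the number of gap admissions to be worth knowing.

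Separately, SAP 3.3 and Protocol 3.4.3 disagree on whether a psychiatric admission during screening excludes a subject. If the SAP rule were applied, the filter would extend to subjects who do not cross-titrate.

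**What to change.** A cheap improvement. Leave the primary analysis unchanged and add to SAP 7.1.3:

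1. A table of the number of subjects with an inpatient psychiatric admission between consent and Day 1, and the number withdrawn for it. Draw it from the hospitalization and utilization record as well as serious adverse events.
2. A sensitivity McNemar analysis in eligible consented subjects who began the switch or went directly to MyCite. Run the post period from consent to consent + 83 days, which is 84 days and matches the retrospective window; adding the screening days to the prospective side alone would bias the other way. Any inpatient psychiatric admission in it is an event, including one that leads to withdrawal.
3. The number of subjects withdrawn for other reasons with incomplete follow-up, with the result shown counting them first as admitted and then as not admitted.
4. For re-screened subjects, retrospective windows anchored at the first consent.

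Also reconcile SAP 3.3 with Protocol 3.4.3 on psychiatric admission during screening.

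**Cost.** SAP wording, one count table and one sensitivity table. Much of the data is already due: hospitalizations are reported throughout the trial (Protocol 3.7.2.1.1), and Month 6/ET evaluations are required for withdrawn subjects unless consent is fully withdrawn (Protocol 3.7.1.3.5). Two limits remain. The sensitivity window includes days on oral aripiprazole before MyCite; with 45 days of screening only 84 − 45 = 39 of its days follow Day 1. Some subjects withdrawn in screening will also lack complete data to consent + 83 days. It should therefore stay a sensitivity analysis.
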